Electronic case report form (eCRF)	Sometimes referred to as clinical report form. A printed or electronic form for recording study participants' data during a clinical study, as required by the protocol.
Effectiveness	Effectiveness is the measure of the produced effect of an intervention when carried out in a clinical environment.
eGFR	Estimated glomerular filtration rate
End of the study	End of study (trial) is the date of the last visit or last scheduled procedure shown in the Study Schedule for the last active patient in the study.

Enrollment	The act of assigning a patient to a treatment. Patients who are enrolled in the trial are those who have been assigned to a treatment.
Enter	The act of obtaining informed consent for participation in a clinical trial from patients deemed eligible or potentially eligible to participate in the clinical trial. Patients entered into a trial are those who sign the informed consent form directly or through their legally acceptable representatives.
GCP	Good clinical practice
GEE	Generalized estimating equation
GMFM-88	Gross Motor Function Measure-88
HBV	Hepatitis B virus
HIV	Human immunodeficiency virus
ICF	Informed consent form
IFN	Interferon
IL	Interleukin
Institutional review board/ethical review board (IRB/ERB)	A board or committee (institutional, regional, or national) composed of medical and nonmedical members whose responsibility is to verify that the safety, welfare, and human rights of the patients participating in a clinical study are protected.
IP-10/CXCL10	Interferon inducible protein 10/ C-X-C motif chemokine 10
ISG	Interferon stimulating genes
IV	Intravenous
IVIg	Intravenous immune globulin
JAK	Janus kinase
Legal representative	An individual, judicial, or other body authorized under applicable law to consent on behalf of a prospective patient to the patient's participation in the clinical study.
MDBP	Myelin Disorders Biorepository Project
Patient	A study participant who has the disease or condition for which the investigational product is targeted.
PH	Pulmonary hypertension
PK	Pharmacokinetic
PPD	Purified protein derivative
QD	Once daily
QLS	Quasi-Least Squares
RA	Rheumatoid arthritis
SAE	Serious adverse event

Screen	The act of determining if an individual meets minimum requirements to become part of a pool of potential candidates for participation in a clinical study. In this study, screening involves diagnostic procedures and/or tests (for example, x-rays, blood draws). For this type of screening, informed consent for these screening procedures and/or tests shall be obtained; this consent may be separate from obtaining consent for the study.
SLE	Systemic lupus erythematosus
STAT	Signal transducers and activators of transcription
STING	Stimulator of interferon genes
SUSAR	Suspected unexpected serious adverse reaction
ТВ	Tuberculosis
Treatment-emergent adverse event (TEAE)	Any untoward medical occurrence that either occurs or worsens at any time after treatment baseline and that does not necessarily have to have a causal relationship with this treatment.
ULN	Upper limit of normal
WBC	White blood cell

ABSTRACT

Context: (Background)

Aicardi Goutières Syndrome (AGS) is a multisystem, heritable disorder of innate immunity resulting in excessive interferon production. Interferon production causes injury to the brain, as well as the skin, liver, lungs, heart and many other organs. Treatment with Janus Kinase (JAK) inhibitors offers the promise of decreasing interferon signaling and limiting the morbidity of this devastating disorder.

Objectives: (Primary and important secondary objectives)

The primary objective is to assess safety as well as efficacy of baricitinib, a JAK inhibitor, in patients with Aicardi Goutières Syndrome. Efficacy will be determined primarily by changes in the AGS scale from baseline to 52 weeks of treatment. The secondary objectives include assessments of safety parameters, of therapeutic endpoints including an AGS symptom diary score; a surrogate biomarker, the interferon signaling gene score; and of functional neurologic measures (including GMFM-88 and longitudinal AGS scale measurements [in addition to and including baseline and 52 weeks]).

Study Design:

Open-label phase 2 clinical study.

Setting/Participants:

The setting: outpatient

The number of sites: single center

The number and description of participants including key eligibility criteria: eligible patients will have AGS with symptoms of neurologic disability, laboratory evidence of AGS related disease, or skin involvement, and no exclusion criteria making the administration of baricitinib less safe.

Clinical care and research procedures will be used to generate data about the use of baricitinib in patients affected by AGS, which may potentially help to improve treatment outcomes for subjects within this patient population.

Study Interventions and Measures:

The research procedures include physical examination, vital signs, symptom diaries (for at least two years from treatment initiation), medical record review, functional neurologic measures such as the GMFM-88 assessment or the AGS scale, assessment of skin inflammation, laboratory evaluations and phlebotomy including PK testing and leftover samples for future research, interferon signaling scores, pregnancy testing, and administration of baricitinib. Throughout the protocol, note that the term "study interventions" includes clinical and research procedures used to generate study data. Main study outcome measures include the AGS scale, symptom diaries, safety monitoring, functional assessments of neurologic function (ie GMFM-88), and interferon signaling gene scores.

PROTOCOL SYNOPSIS

Name of Investigational Product:	Baricitinib, orally or G-tube administered
Title of Study:	Janus Kinase Inhibitor (Baricitinib) for Aicardi Goutières Syndrome
Length of Study:	Each patient may be treated up to 288 weeks.
Number of Planned Patients/Subjects:	Entered: up to 55 Enrolled: up to 55 Completed: up to 55
Study Objective:	To assess safety and efficacy of baricitinib in individuals affected by Aicardi Goutières Syndrome
Study Population and Main Eligibility/ Exclusion Criteria:	Individuals with Aicardi Goutières Syndrome with evidence of AGS related neurologic or systemic disease and without systemic medical problems placing them at higher risk for treatment with baricitinib.
Primary Outcome Measures:	The primary objective is to determine if the administration of baricitinib to patients with AGS results in an improvement or stability of the AGS scale from baseline to 52 weeks.
Secondary Outcome Measures:	Secondary objectives will include assessments of safety parameters, improvement of interferon signaling scores, improvement of AGS scale (longitudinal) and GMFM-88, and improvement of a daily disease severity scale, for the duration of the treatment period.

[figure not shown]
Study Design:	Open- label, phase 2 clinical study.
Statistical Considerations (sample size and analysis plan):	The change over time in AGS scale will be compared pre and post treatment with a GEE analysis that accounts for age at treatment initiation. Sensitivity analyses will also be performed, to evaluate the efficacy of treatment across several statistical approaches with varying assumptions. Sample size considerations were based on preliminary data. In preliminary data, the average of within subject changes (post-treatment average minus pre-treatment average) was 0.80 with a standard deviation of changes of 1.04. This corresponds to an effect-size of 0.80/1.04 = 0.77. From PASS 16, a sample size of 30 data pairs achieves 98.3% power to reject the null hypothesis of zero effect size when the population effect size is 0.77 and the significance level (alpha) is 0.050 using a two-sided paired t-test. Should the effect- size be smaller than we observed in our preliminary data, we will have 80% power to detect an effect size of 0.53, which corresponds to an average of within subject changes of 0.55, if the SD of changes is 1.04.
Funding Sponsors (federal, state, foundation and industry support):	Drug and grant support provided as a donation by Eli-Lilly Secondary funder: Pennsylvania Department of Health

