6.3.2 Primary Outcome Analysis

As is often the case in a study of a rare disease, we face a number of challenges in our analysis. The number of available patients with AGS is limited, so that our sample size is small. This protocol grew out of a compassionate use trial, so that randomization could not be employed to assign patients to receive treatment (or not). The temporal spacing of measurements differs between treated patients versus historical controls. As a result of these features, there are limitations to many of the standard statistical approaches. Our approach will therefore be to apply a recommended approach for efficacy, but to also apply several sensitivity analyses. Our goal will be to demonstrate efficacy for several statistical approaches, as we achieved in our analysis of preliminary data.

Our efficacy analysis for our primary outcome will apply the method described in Section 15.4 of Fitzmaurice, Laird, & Ware⁷⁴ that decomposes longitudinal effects of treatment versus cross-sectional effects due to participants starting treatment at different ages. We will first create a time for each patient that is negative prior to treatment and is positive after treatment. We will then fit a GEE model that includes time within patients, an indicator variable for treatment and a time by treatment interaction term. If the interaction term is significant, this will indicate that the change over time in AGS score (slope) is different after treatment, versus before. If the interaction term is not significant, it will be removed and the model will be fitted with time and the indicator variable for (post) treatment. If the indicator variable differs significantly from zero, this will indicate that the AGS score is higher on average, post-treatment. To compare values at baseline and 52 weeks post baseline, different parameterizations of time (continuous versus indicator variables at different visits) will be considered and analyses will also be performed on data restricted to values measured at baseline and 52 weeks post baseline. This approach will first be applied to patients who are eventually treated. to compare their AGS scores pre versus post-treatment.

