6.3.3 Secondary Outcome Analysis

6.3.3.1 Longitudinal analysis of the AGS scale

In secondary analysis, we will include historical controls in the GEE models described in section 6.3.2; the "age at treatment" (time zero) for controls will be their age at their final encounter. The GEE models will also adjust for confounders (e.g. age of the subject, length of disease, and genotype⁷⁵) especially variables that were identified as being related to receiving treatment (see Section 6.3.1). We will fit several working correlation structures to model the association between the repeated measurements on each patient, and will use goodness of fit criteria for GEE to choose between the structures. Goodness of fit criteria will also be used to compare fit of models (e.g. for models that include time as a continuous variable versus a series of indicator variables for visit).

In addition to GEE, we will fit quasi-least squares (QLS) regression models.⁷⁶ QLS is a computational approach for estimation of the correlation parameters in the framework of GEE that can be applied should GEE fail to converge, or to fit correlation structures that are not available in the framework of GEE. For example, the Markov correlation structure that is plausible for unequally spaced data is not available in the **xtgee** command for implemention of GEE in Stata.

In addition to the GEE analysis that includes historical controls, we will implement several sensitivity analyses that are described in the Table below. These methods were successfully implemented in analysis of our preliminary data.

Table 2. Statistical Approaches				
Question to be Evaluated in Sensitivity Analysis	Statistical Approach			
For each patient who was eventually treated, if we obtain their average of their AGS scale values prior to treatment (pre-treatment average) and the average of their AGS scale values after treatment (post- treatment average), are the post-treatment averages higher than the pre-treatment averages?	Compute the average of the within subject changes (post-treatment average minus pre-treatment average) with 95% CI; apply the paired t-test to compare the mean of pre-treatment to the mean of post-treatment averages within patients.			

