Is the average AGS scale value higher after treatment than before treatment, when we modify the previous analysis to include patients who were never treated, by calculating their pre-treatment average AGS scale as the average of all of their AGS scale values?	GEE analysis in which patients who were treated contribute two measurements (pre-treatment average and post-treatment average), while patients who were never treated contribute one measurement ("pre-treatment" average of AGS scale). The GEE model will include an indicator variable for post-treatment and use an exchangeable correlation structure to account for the intra- subject correlation of measurements on each patient.			
Does the AGS scale at screening differ from the final value within patients?	Paired t-tests or non parametrics Wilcoxon signed-rank test will be applied as appropriate to compare the screening and final values within patients.			

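### Section 6.3.2 omits the age-at-treatment-initiation term that the synopsis promises, so under some working correlations starting-age differences can appear as a false change of slope

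*Combined protocol and SAP*

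**What the plan says.** The synopsis (Statistical Considerations) says that the AGS scale "will be compared pre and post treatment with a GEE analysis that accounts for age at treatment initiation". Section 6.3.2 repeats the aim, citing a textbook method that "decomposes longitudinal effects of treatment versus cross-sectional effects due to participants starting treatment at different ages".

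Section 6.3.2 then sets out the model. The time origin is the start of treatment: "We will first create a time for each patient that is negative prior to treatment and is positive after treatment". The terms follow: "We will then fit a GEE model that includes time within patients, an indicator variable for treatment and a time by treatment interaction term". A non-significant interaction is dropped, which leaves time and the post-treatment indicator. Age at initiation is in neither model.

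Section 6.3.2 names no working correlation. Section 6.3.3.1, on secondary analysis, says: "We will fit several working correlation structures to model the association between the repeated measurements on each patient", with goodness of fit deciding between them. It remarks that "the Markov correlation structure that is plausible for unequally spaced data is not available in the" Stata GEE command, and offers quasi-least squares as the way to fit it. One sensitivity GEE in Table 2 is to "use an exchangeable correlation structure to account for the intra- subject correlation".

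Age adjustment is written out only for the secondary analysis with historical controls: "The GEE models will also adjust for confounders (e.g. age of the subject, length of disease, and genotype", and so on.

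**The concern.** With time set to zero at treatment start, nothing in the listed model carries starting age. A child who starts at 10 years can supply scores far to the left of zero; a child who starts at 1 year cannot. Early pre-treatment times are therefore populated mainly by late starters, while post-treatment times are populated by everyone. If late starters have systematically different AGS levels, the fitted pre-treatment line is tilted by who contributes to it, and the tilt disappears after treatment. That is a change of slope with no change in any patient.

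The interaction is the first test in the primary efficacy model. At stake is whether a significant result reflects the drug or the mix of starting ages, and whether the answer turns on a correlation structure that has not been fixed.

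**Working it through.** **1. The plan's own figure.** The sample size rests on a two-sided paired t-test with 30 pairs, effect size 0.80/1.04 = 0.77 and alpha 0.05. With noncentrality 0.77 × √30 = 4.22 on 29 degrees of freedom, power is 98.27% (stated 98.3%). Power of 80% is reached at effect size 0.529 (stated 0.53), and 0.53 × 1.04 = 0.55. These figures are correct and do not depend on this point.

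**2. Mechanism.** Suppose there is no drug effect and no within-patient change:

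Y = a + γ·A + b + e,

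where A is starting age, γ the gradient in AGS points per year of starting age, b a patient effect and e residual error. Under independence, the bias in each listed coefficient is γ times that coefficient in a regression of A on time, indicator and product. Since t ≥ −A, mean starting age rises as t becomes more negative, so the pre-treatment slope of A on t is negative. After treatment it is about zero if follow-up does not depend on A. The product coefficient is then positive, and the bias takes the sign of γ.

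**3. Inputs.**
- From the documents: about 45 evaluable treated patients (6.4); entry from 1 month of age (3.3.2); retrospective scoring from clinical notes is possible (1.5); follow-up to 288 weeks, about 5.5 years (3.2.1).
- Assumed, because the documents do not give them: γ of 0, 0.2 or 0.4; starting age uniform over 0.5-12 years; patient SD 2.0 and residual SD 0.8 (intraclass correlation 4/(4 + 0.64) = 0.86); 1-10 pre-treatment scores, more in older starters, spread over life before treatment.
- Sandwich standard errors with a small-sample correction; 200 replicates. Monte Carlo error is √(0.05 × 0.95/200) = 1.5 percentage points at a 5% rate and √(0.415 × 0.585/200) = 3.5 points at 41.5%.

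**4. Interaction test, 5.5-year follow-up, no drug effect.**

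| γ | Structure | Bias as written (points/year) | False positives as written | With age at initiation |
|---|---|---|---|---|
| 0 | independence | +0.008 | 4.0% | 3.5% |
| 0 | Markov | −0.001 | 5.5% | 4.5% |
| 0 | exchangeable | +0.001 | 4.0% | 3.5% |
| 0.2 | independence | +0.106 | 37.5% | 3.5% |
| 0.2 | Markov | +0.046 | 15.5% | 4.5% |
| 0.2 | exchangeable | +0.002 | 4.0% | 3.5% |
| 0.4 | independence | +0.203 | 88.5% | 3.5% |
| 0.4 | Markov | +0.083 | 41.5% | 4.5% |
| 0.4 | exchangeable | +0.002 | 4.0% | 3.5% |

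The independence bias is proportional to γ, as step 2 requires: (0.106 − 0.008)/0.2 = 0.49 and (0.203 − 0.008)/0.4 = 0.49.

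A second simulation with the same sample size, gradients and follow-up gave about 30% and 80% under independence, 14% and 39% under Markov, and 4-7% under exchangeable. All were 4-7% once the age term was added. This is the source of the lower ends of the ranges quoted.

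**5. Where the effect is small, γ = 0.4** (in the order independence, Markov, exchangeable).
- Interaction, 1-year follow-up: 8.5%, 5.5%, 6.0%.
- Treatment indicator (reduced model), 1 year: 16.5% (bias +0.21 points), 5.5% (+0.02), 3.5% (+0.01). With the age term: 6.5%, 4.0%, 2.5%.
- Treatment indicator, 5.5 years: 11.0%, 6.0%, 4.0%. With the age term: 5.0%, 4.0%, 3.5%.
- Identical visit times for all patients (indicator model): no bias, and the same estimates with and without the age term.

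**6. Within-patient comparisons.** In a difference of two scores on the same patient, γ·A cancels. The complete-pair baseline/52-week analysis and the paired tests in Table 2 are therefore not affected.

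**The case against.** **The citation may already supply the term.** Section 6.3.2 commits to a named method whose stated purpose is this decomposition, and it says what the model includes, not that nothing else enters. A reader might infer that the adjustment will certainly be left out. The documents do not establish that, and the cited text is not available to check. What stands is that the terms are spelled out for both models, that these terms cannot perform the decomposition, and that someone programming from 6.3.2 would not deliver what the synopsis promises.

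**The largest rates belong to independence, which the plan never names.** This is correct, and those rates should be read as conditional on that choice. Markov is named, but in a secondary-analysis section. Under Markov the inflation appears in the interaction test with long follow-up; the indicator, and the 1-year interaction, are near nominal. A reader might infer a false step in AGS level under Markov; the calculations do not show one.

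**The gradient is assumed.** A reader might infer a false treatment effect of most of a point. One set of assumptions, with 0.5 points per year over starting ages 0.2-15, does give +0.79 points and 69% false positives for the indicator under independence. But that gradient implies 0.5 × 14.8 = 7.4 points on a 0-11 scale from starting age alone. A different assumed visit pattern at the same gradient gave +0.29 to +0.36 points and 11-17%. In the first case 10% false positives remained after adding the age term, so part of the 69% is not due to the missing covariate. Nothing in the documents supports that figure as an estimate.

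**The 52-week endpoint has protected analyses.** This also stands (step 6). It does not protect the full longitudinal model, which 6.3.2 presents first, with the restricted analysis as an addition.

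**Conclusion.** The mismatch between the synopsis and 6.3.2 is plain: age at treatment initiation is promised and is in neither written model. It matters if three things hold together: AGS level varies with starting age, visit times depend on starting age, and the working correlation lets between-patient differences into the contrast. The second is close to built in. The first is the risk that 6.3.2 itself sets out to address, but its size is unknown. The third is left open.

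Over the assumed 0.2 to 0.4 points per year, with follow-up to 5.5 years, the false-positive rate of the interaction test is about 30-89% under independence, about 14-42% under Markov and about nominal under exchangeable. With a zero gradient there is no inflation. The exchangeable result comes from data generated with a strong patient effect (intraclass correlation 0.86).

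A reader might infer that the baseline-to-52-week result is compromised, or that exchangeable must be imposed. Neither follows. Complete-pair comparisons are unaffected, and the plan gives a reason, unequal spacing, for considering Markov. The point is an incomplete specification with a possibly large effect on one test, not a demonstrated bias in the trial's result.

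**What to change.** In 6.3.2, write age at treatment initiation into both models, to match the synopsis:

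- Full: intercept + age at initiation + time since initiation + post-treatment indicator + time × indicator.
- Reduced: the same without the product.

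Date of birth is already abstracted (5.1.7 and 5.2.15) and the start of treatment defines time zero, so no new data are needed. The cost is a wording change and one extra parameter with about 45 patients. In the simulations the term brought every structure back to about nominal, but there the age gradient was linear by construction. A linear term will not remove bias from non-linear development with age. The choice of working correlation can stay with the sponsor; stating it for the primary fit would be helpful but is not needed to close this point.

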1 BACKGROUND INFORMATION AND RATIONALE

1.1 Introduction

The purpose of this immediate and delayed phase study protocol is to establish safety and efficacy of baricitinib in individuals with **Aicardi Goutières Syndrome (AGS)**, a heritable disorder of excessive interferon (IFN) production, occurring in fewer than 1/7000 live births¹, that affects brain, skin, bone marrow and visceral organs. This rare condition is well positioned for new therapeutic innovations due to growing interest in targeting interferon pathways also implicated in more common disorders such as lupus and rheumatoid arthritis. In addition, AGS is increasingly well characterized, with an established course of disease², improved early recognition through laboratory criteria^{3,4}, MRI^{2,5}, and well characterized genotyping⁶⁻⁹. Genetic abnormalities in viral sensing genes

(TREX1. RNASEH2A. RNASEH2B. RNASEH2C, SAMHD1, ADAR1, IFIH1⁶⁻⁹) trigger an endogenous IFN response resulting in extensive end organ damage. (Figure 1). IFNs, increased in blood and cerebrospinal fluid in AGS^{10,11}, are thought to be directly responsible for disease pathology. Transgenic animal models of IFN overexpression in astrocvtes demonstrate thrombotic а microangiopathy¹², similar to pathology seen in AGS brain and skin lesions¹³⁻¹⁵. There is evidence of vascular injury in vitro in vascular endothelial cells exposed to IFN¹⁴ and in humans treated with recombinant IFN¹⁶, suggesting tissue specific injury. New data suggests that treatment with IFN blockade using

Janus Kinase (JAK) inhibitors may be beneficial in interferon mediated disorders. Since opening our expanded access use program for baricitinib, a JAK inhibitor, in February 2017, we have enrolled more than twenty individuals. Preliminary data^{17,18} suggests improvement in patient reported scores and expression of IFN signaling genes, however, more comprehensive and longer-term study is needed to assess clinical benefit of this therapeutic approach.

Aicardi-Goutières Syndrome (AGS) is an inflammatory disease particularly affecting the brain (causing severe damage to the white matter as well as the deposition of calcium in both white and grey matter) and the skin (resulting in so- called chilblain lesions affecting the toes, fingers and ears in particular), but also demonstrating systemic features (for example, glaucoma, cardiomyopathy, pulmonary hypertension, myopathy, neuropathy, endocrinologic problems) in many patients. All available literature sources suggest that the prevalence of AGS is well below 5 in 10,000 persons.

AGS is a genetically heterogeneous Mendelian disease, occurring due to mutations in any of the genes encoding the DNA exonuclease TREX1 (TREX1), the three non- allelic components of the RNase H2 endonuclease complex (RNASEH2A, RNASEH2B, and RNASEH2C), the deoxynucleoside triphosphate triphosphohydrolase SAMHD1 (SAMHD1), the double-stranded RNA editing enzyme ADAR (ADAR), and the double-stranded RNA cytosolic sensor IFIH1/MDA5 (IFIH1).

[figure not shown]
The proteins defective in AGS are all associated with nucleic acid metabolism/ sensing. It is hypothesized that six of these proteins are involved in limiting the accumulation (TREX1, the three RNase H2 complex components, SAMHD1), or the nature (ADAR), of intracellular nucleic acid species, a failure of which process results in triggering an innate immune response that is more normally induced by viral nucleic acids. The seventh protein, IFIH1/MDA5, is also involved in nucleic acid metabolism, being a receptor for cytosolic dsRNA. This understanding defines a novel cell-intrinsic mechanism for the initiation of autoimmunity by interferon-stimulatory nucleic acids and offers an elegant mechanistic explanation for the phenotypic overlap of AGS with congenital infection and systemic lupus erythematosus (SLE). That is, in the absence of AGS-related protein activity, endogenous nucleic acids accumulate and are sensed as viral or "non- self," leading to the induction of an interferon alpha-mediated immune response and, sometimes, the production of antibodies against self-nucleic acids.

AGS is associated with increased levels of interferon alpha in the cerebrospinal fluid (CSF) and serum. However, interferon alpha levels, and white cell counts, in the CSF have been reported to fall over the first few years of life, perhaps corresponding with an apparent clinical "burning-out" of the encephalopathic period. Unfortunately, due to the obvious difficulties of repeat CSF sampling, very few serial data are available (that is, systematic interferon alpha activity profiling beyond infancy has not been undertaken). Indeed, data acquired more recently on more than 200 AGS patients using qPCR analysis of interferon stimulated genes (ISGs) indicates the presence of a so-called "interferon signature" at any age in almost 100% of patients with mutations in *TREX1, RNASEH2A, RNASEH2C, SAMHD1, ADAR,* and *IFIH1*. Around 30% of patients with *RNASEH2B* mutations demonstrated no such upregulation—but as ISG sampling in these studies was usually performed many years after initial diagnosis, it remains possible that most patients exhibit a positive interferon signature in the early stages of the disease. Whatever the case, these findings are important in indicating an ongoing biochemical disease process which is likely life-long in most patients.

Most characteristically, AGS manifests as an early-onset encephalopathy that results in severe intellectual and physical handicap. A subgroup of infants with AGS present at birth with abnormal neurologic findings, hepatosplenomegaly, elevated liver enzymes, and thrombocytopenia, a picture highly suggestive of congenital infection. Otherwise, most affected infants present at variable times after the first few weeks of life, frequently after a period of apparently normal development. Typically, affected infants demonstrate the subacute onset of a severe encephalopathy characterized by extreme irritability, a loss of previously acquired skills, and a slowing of head growth. Over time, as many as 40% develop chilblain-like skin lesions on the toes, fingers, and ears. Additional phenotypes are now being identified and include later onset disease after a year of age.¹⁹ Of specific note here, mutations in *ADAR* have recently been described in a clinically distinct phenotype characterized by bilateral striatal necrosis. Furthermore, mutations in *RNASEH2B, ADAR* and *IFIH1* can cause non-syndromic spastic paraparesis in the presence of completely normal brain and spinal imaging, indicating that type I interferons can have a neurotoxic effect at the cellular level in the

absence of obvious neuroimaging changes. Most recently, IFIH1 gain-of-function mutations have been shown to cause a phenotype variably characterized by dental anomalies (early-onset periodontitis and root resorption), aortic and valvular calcification, glaucoma, psoriasis, contractures and acro-osteolysis²⁰.

Thus, although a minority of children are affected by the time of birth (that is, the disease has an in-utero onset), most experience the onset of disease at some point post-natally, often after a period of apparently normal development¹⁹. Moreover, disease progression is subacute, reflected in a progressive loss of skills occurring over several months. Thus, a window of opportunity exists during which treatments might be efficacious. Maximum benefit will likely be afforded when effective treatment is started as early as possible after disease onset. However, long-term/later-onset morbidities also occur, for example, chilblains, so children of any age might potentially benefit from efficacious treatment.

